Smoking history	X													

[figure not shown]
Periods	Screening		Treatment Period										Post Treatment Follow Up	Notes
	Week	-10 to -2	-2 ¹ (no later than) ²	BSL	2	4	8	12	16	24	32	40	48 ¹⁶ TD/EOT	
Vital signs	X	X	X	X	X	X	X	X	X	X	X	X	X	X
12-lead ECG ⁴	X								X				X	
Liver Biopsy ¹⁴		X											X	Biopsy to be performed no later than 2 weeks prior randomization
Adverse Events / Serious AE	X	X	X	X	X	X	X	X	X	X	X	X	X	X

[figure not shown]
Periods	Screening		Treatment Period										Post Treatment Follow Up	Notes
	-10 to -2	-2 ¹ (no later than) ²	BSL	2	4	8	12	16	24	32	40	48 ¹⁶ TD/EOT	52 EOS	
Modified AUDIT questionnaire ¹⁵		X	X	X	X	X	X	X	X	X	X	X	X	
Randomization via IRT			S											
Contact IRT	X	X	X	X	X	X	X	X	X	X	X	X	X	
Drug dispensing			S		S	S	S	S	S	S	S	S		
Drug administration record			X		X	X	X	X	X	X	X	X		
Drug compliance					S	S	S	S	S	S	S	S		
AHA Diet Review			S		S		S	S	S	S	S	S	S	
Diet Compliance			X				X		X			X	X	
Exercise assessment			S				S		S			S	S	
Blood collection														
Hepatitis serology ⁵	X													
Liver tests	X	X	X	X	X	X	X	X	X	X	X	X	X	
Serum BUN and Creatinine	X		X		X	X	X	X	X	X	X	X	X	
Coagulation panel	X	X	X				X		X			X		Only INR at screening visit 2

Periods	Screening		Treatment Period										Post Treatment Follow Up	Notes
	Week	-10 to -2	-2 ¹ (no later than) ²	BSL	2	4	8	12	16	24	32	40	48 ¹⁶ TD/EOT	
Hematology	X		X				X		X		X	X	X	
Clinical chemistry panel ⁷	X		X				X		X		X	X	X	
HbA1c	X													

Periods	Screening		Treatment Period										Post Treatment Follow Up	Notes	
	-10 to -2	-2 ¹ (no later than) ²	BSL	2	4	8	12	16	24	32	40	48 ¹⁶ TD/EOT			52 EOS
Urine															
Dipstick / routine Urinalysis with Reflex Micro	X		X		X	X	X	X	X	X	X	X	X	X	
Serum pregnancy test ¹²	X														
Urine pregnancy test ¹²		S	S	S	S	S	S	S	S	S	S	S	S	S	The urine pregnancy test should be performed every 4 weeks up to the follow up visit, including at week 20, 28, 36 and 44, and during any treatment extension period.
Drug screen	X		X												
Study Completion Form	X														

Periods	Screening		Treatment Period										Post Treatment Follow Up	Notes
	Week	-10 to -2	-2 ¹ (no later than) ²	BSL	2	4	8	12	16	24	32	40	48 ¹⁶ TD/EOT	

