9.5 Analysis of secondary variables

9.5.1 Efficacy variables

An overview of the secondary efficacy variables and planned analysis is given in [Table 9-2](#).

Table 9-2 Secondary efficacy variables and analyses

Variable	Analysis
At least a one point improvement of fibrosis	Cochran-Mantel-Haenszel test controlling for baseline fibrosis stage for each tropifexor + CVC combination vs. each monotherapy treatment, with supporting information from risk differences, odds ratios with 95% confidence intervals
Resolution of steatohepatitis (as determined by central pathologist)	Cochran-Mantel-Haenszel controlling for baseline fibrosis stage for each tropifexor + CVC combination vs. each monotherapy treatment, with supporting information from risk differences, odds ratios with 95% confidence intervals

There is a single secondary objective in this study which is to characterize the efficacy of tropifexor + CVC in patients with NASH with fibrosis stage F2/F3 as assessed by histological improvement after 48 weeks of treatment compared to monotherapies (tropifexor and CVC) relative to baseline biopsy. There are two estimands that will be used to evaluate this objective.

The first estimand is the difference on the proportion of patients on the different tropifexor + CVC regimens who achieve at least a one point improvement in fibrosis at Week 48 compared to tropifexor and CVC monotherapy patients. It is assumed that anyone who does not have a Week 48 liver biopsy or does not remain on their randomized study treatment for at least 24 weeks (even if a Week 48 biopsy was obtained) will have their outcome imputed by multiple imputation (MI). For subjects who remain on their randomized study treatment for at least 24 weeks, but discontinue study treatment prior to Week 48, available Week 48 biopsy results will be used as observed. This is a hypothetical strategy addressing the question “what would be the outcome if subjects had stayed at least 24 weeks on treatment and a Week 48 biopsy had been obtained”. Treatment differences between tropifexor + CVC combination therapy and monotherapy with tropifexor or CVC will be evaluated using a Cochran-Mantel-Haenszel test controlling for baseline fibrosis stage (F2/F3). The estimand will be evaluated in the FAS population.

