### **2.7.3 Handling of missing values/censoring/discontinuations**

Missing baseline data (if applicable) for the secondary endpoints will not be imputed.

Missing follow-up data for the secondary endpoints will be handled as follows:

If a patient stayed on randomized study treatment for less than 24 weeks, missing data will not be imputed, and if data are available (which is not expected as per protocol) they will not be included in the analysis.

If a patient stayed on randomized study treatment for at least 24 weeks, but follow-up data are not available, data will be imputed by multiple imputation (see Section 5.1.4).

[figure not shown]
If a patient stayed on randomized study treatment for at least 24 weeks, and follow-up data are available, data will be used as observed, even if treatment was discontinued prior to Week 48.

Due to the COVID-19 pandemic, it was not possible for some patients to return in time for the Week-48 visit to perform a liver biopsy. Instead, it was possible for additional treatment to be dispensed (see drug dispensing plan in Section 5.5.2 in the protocol), and the Week-48 liver biopsy could be delayed up to approximately 12 weeks. Since the purpose of the secondary efficacy analysis is to evaluate the potential histological benefit of study treatment, all biopsies obtained, including those from eligible patients after Week 48, will be included in the analysis as Week-48 biopsies.

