### **5.1.4 Other imputations**

A multiple imputation approach will be applied to missing follow-up biopsies.

For subjects who do not have a Week 48 liver biopsy or not remain on their randomized study treatment for at least 24 weeks (even if a Week 48 biopsy was obtained), the biopsy based outcomes will be imputed by multiple imputation (MI). It is assumed that biopsy results are missing at random (MAR). Available results for subjects who discontinue treatment before 24 weeks are set to missing for this analysis. Imputation will be based on available results from subjects who did not discontinue study treatment, thus addressing the question what the results would have been if subjects had not discontinued. The imputation model will take into account the treatment group, the baseline fibrosis stage (categorical), [REDACTED], the baseline ALT, [REDACTED] and change in ALT, [REDACTED] from baseline to Week 12 and to Week 24 (continuous). As there is only one post-baseline biopsy assessment, an arbitrary missing pattern is assumed and a fully conditional specification (FCS) method with logistic regression is applied. The randomization seed is 4572201 and the number of imputations will be set to 50.

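### SAP 5.1.4 imputes missing biopsies under a different hypothetical question from protocol 9.5.1 and, read literally, bars late stoppers' biopsies from informing the imputation

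*SAP*

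**What the plan says.** Protocol 9.5.1 imputes the outcome of any patient who has no Week 48 biopsy or had less than 24 weeks on randomized treatment. Its stated question is "what would be the outcome if subjects had stayed at least 24 weeks on treatment and a Week 48 biopsy had been obtained". For patients who reach 24 weeks "but discontinue study treatment prior to Week 48, available Week 48 biopsy results will be used as observed". The second estimand follows the same rules.

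SAP 2.7.3 agrees about late stoppers who have a biopsy: "data will be used as observed, even if treatment was discontinued prior to Week 48". For patients with at least 24 weeks on treatment "but follow-up data are not available, data will be imputed by multiple imputation", with SAP 5.1.4 giving the method.

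On the source of the imputations, SAP 5.1.4 says "Imputation will be based on available results from subjects who did not discontinue study treatment". It presents that choice as "thus addressing the question what the results would have been if subjects had not discontinued". It assumes missing at random. Its visible predictors are treatment group, baseline fibrosis stage, baseline ALT, and the changes in ALT to Weeks 12 and 24; other predictors are redacted. SAP Section 4 lists three changes to the protocol analyses, and this is not one of them.

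**The concern.** The protocol's question allows a patient to stop after Week 24. The SAP's question does not. If the donor sentence is programmed as written, stopping between Weeks 24 and 48 is handled in two ways, depending only on whether a biopsy was obtained. Take two patients who both stop at Week 30. The one with a biopsy contributes the result as it stands. The one without is imputed from patients who never stopped, and the first patient's biopsy plays no part in that imputation.

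If late stoppers respond less often than completers, an arm's imputed rate rises with its late stopping and its missing biopsies. If those differ between arms, so does the upward shift, and the difference in response rates moves with it.

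**Working it through.** **1. The texts side by side**

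| | Protocol 9.5.1 | SAP 2.7.3 | SAP 5.1.4 |
|---|---|---|---|
| Question | At least 24 weeks on drug, biopsy obtained | Not stated | No discontinuation |
| Stopped Weeks 24–48, biopsy available | Observed | Observed | Not an imputation source, if read literally |
| At least 24 weeks on drug, no biopsy | Imputed, source not specified | Imputed | Imputed from non-discontinuers |

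**2. The plan's own figures, for scale.** Protocol 9.8.2 gives power of 81% (69% vs 42%) and 95% (69% vs 35%) with 50 per arm and two-sided alpha 0.10. With the continuity correction, taking n0 = n(1 − 1/(nd))² for n = 50 and difference d, I obtain 81.7% and 95.1%. These figures are not in dispute.

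**3. Effect of the donor rule on one arm.** Let m be the share of the arm imputed, l the share of late stoppers with a biopsy, and c = 1 − m − l the share of completers with a biopsy. Let pc and pl be the response rates in completers and late stoppers. Covariates are ignored.

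- Completers only as donors: c·pc + l·pl + m·pc
- All biopsied patients with at least 24 weeks as donors: c·pc + l·pl + m·(c·pc + l·pl)/(c + l)
- Difference: m · l/(1 − m) · (pc − pl)

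The documents give none of m, l or the gap pc − pl, so these are assumptions:

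| m | l | Gap (points) | Shift in arm rate (points) |
|---|---|---|---|
| 5% | 5% | 10 | 0.05 × 0.05/0.95 × 10 = 0.03 |
| 10% | 10% | 30 | 0.10 × 0.10/0.90 × 30 = 0.33 |
| 20% | 15% | 30 | 0.20 × 0.15/0.80 × 30 = 1.1 |
| 30% | 15% | 50 | 0.30 × 0.15/0.70 × 50 = 3.2 |

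**4. Effect on the difference between arms**

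- Same m, l and gap in both arms: 0.
- Combination 20%/15%, monotherapy 10%/5%, gap 30: 1.13 − 0.17 = 0.96 points (24.0 against 23.0).
- Combination 30%/15%, monotherapy 5%/5%, gap 30: 1.93 − 0.08 = 1.85 points.

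**5. Scale.** At the planned 69% vs 42% with 50 per arm, the standard error of the difference is √[(0.69 × 0.31 + 0.42 × 0.58)/50] = 0.096, or 9.6 points. One patient is 2% of an arm.

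**6. What pooling alone does not do.** If late stoppers become donors without a term for stopping, the Week 30 patient is still imputed mostly as a completer, and a completer who missed only the biopsy is pulled toward the stoppers. With such a term, the correction falls on the right patients. The shift in an arm is then u × (pc − pl), where u is the share of the arm that stopped between Weeks 24 and 48 and has no biopsy.

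**7. Markers after Week 24.** Protocol Table 6-1 schedules liver tests at Weeks 32, 40 and 48, and the visible model uses none of them. A simulation of 400,000 patients shows what this could cost. It assumed log-odds of a missing biopsy of 0.5 per SD of Week 48 ALT, a response odds ratio of 2 per SD, and a Week 24/48 correlation of 0.5. The Week 24 model was biased by about 1.1 to 1.3 points per arm. Adding the Week 48 value reduced this to about 0 if that value was always available and to about 0.5 if it was missing for half of those without a biopsy. There was no gain (1.0 to 1.3) if it was missing for all of them.

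**The case against.** The strongest reply is that the donor restriction is only one reading. The sentence just before it sets to missing only the biopsies of patients who stopped before Week 24, so not discontinuing may refer back to that threshold. No step removes the biopsies of later stoppers, and a fully conditional specification run on the SAP 2.7.3 data would use them unless they were deliberately dropped. This stands as an ambiguity. It does not dispose of the point, because the donor sentence and the question that follows it both carry no time limit. Two programmers could implement different analyses.

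Second, the protocol fixes no imputation source, and completers also satisfy its 24-week condition. This stands too. The figures above are distances between two donor rules, not bias against a single true value. For completers who missed only the biopsy, completers are the better source.

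Third, SAP 2.7.2 describes treatment as taken for 48 weeks, which fits the SAP's question. However, it names no strategy for discontinuation, and SAP 2.7.3 still takes late stoppers as observed.

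A reader might go further and infer that the SAP discards observed outcomes. It does not: late stoppers' biopsies enter the analysis under both documents, and the literal exclusion affects only the imputation step. A reader might also infer that the Week 24 marker cut-off is a material flaw. The documents do not support that. The Week 48 liver test belongs to the same visit as the biopsy. Protocol Section 6 lists no laboratory tests among the checks at remote COVID-19 visits, and Section 5.5.2 asks for tests during a treatment extension only where feasible. Patients stopped before Week 24 have no later on-treatment values, and some predictors are redacted.

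**Conclusion.** The mismatch in the question is plain on the text, undeclared in SAP Section 4, and applies to both histology endpoints. The exclusion of late stoppers as donors follows from a literal reading and needs at least a clarification. Under the assumed rates the effect is about 0 to 3 points per arm and 0 to 2 points between arms. It is nil between arms if missingness, late stopping and the response gap are equal, and its direction assumes that late stoppers respond less often. Against a standard error near 9.6 points, and for secondary analyses in a trial whose primary objective is descriptive safety, this is modest. It should still be corrected, because it can shift the comparison when late stopping differs between arms and the remedy needs no new data.

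SAP 2.7.3 and 5.1.4 also disagree on whether patients with less than 24 weeks on treatment are imputed at all. That is a separate conflict. Patients with at least 24 weeks and no biopsy are imputed under either rule, so this point does not depend on it.

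**What to change.** In SAP 5.1.4:

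1. Restate the protocol 9.5.1 question.
2. Fit the imputation model to every biopsy that enters the analysis, that is, all patients with at least 24 weeks on treatment, including those who stopped later.
3. Where numbers allow, include an indicator or duration term for stopping between Weeks 24 and 48, so that completers who missed only the biopsy are still imputed as completers. If patients with less than 24 weeks are imputed, state which value of this term they take, since the protocol's question leaves it open.

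If the sponsor prefers the SAP's question, declare it in SAP Section 4 and align SAP 2.7.3 with it.

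A smaller, optional step is to add one late marker term: the last on-treatment change in ALT after Week 24. It helps only where those values exist for patients without a biopsy.

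The cost is SAP wording and a few lines of imputation code. The stopping term may be poorly estimated if few late stoppers have biopsies. The marker adds one more partly missing covariate to a model with about 48 patients per arm (193 randomized, divided by four).

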## **5.2 AEs coding/grading**

AEs are coded using the MedDRA dictionary, and severity is graded mild/moderate/severe.

## **5.3 Laboratory parameters derivations**

### **5.3.1 Laboratory parameters**

Liver laboratory events will be classified in two ways:

- Events as defined in Appendix 2 of the protocol (Table 14-1). Only the laboratory results criteria will be considered. Confirmation of the results is not taken into account. For Table 14-1, criteria of ALT and AST are evaluated as either-or relationship, while those of baseline and treatment-emergent assessments as both-and relationship.
- Events as defined in the internal Novartis “Analysis plan for liver safety data”, Table 6-1.

[figure not shown]
Renal laboratory events will be classified in two ways:

- Events as defined in Appendix 3 of the protocol (Table 15-1). Only the laboratory results criteria will be considered. Confirmation of the results is not taken into account.
- Events as defined in the internal Novartis “Analysis plan for renal safety data”,

Criteria for other laboratory parameters:

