7.4 Renal safety monitoring

The following two categories of abnormal renal laboratory values have to be considered during the course of the study:

- Serum event:
 - confirmed (after ≥ 24 h) increase in serum creatinine of $\geq 25\%$ compared to baseline during normal hydration status
- Urine event
 - new onset ($\geq 1+$) proteinuria;
 - new onset ($\geq 1+$), hematuria or glycosuria

Every renal laboratory trigger or renal event as defined in [Table 15-1](#) in [Appendix 3](#) should be followed up by the investigator or designated personnel at the trial site as summarized in [Appendix 3](#).

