9.5.2.2 Laboratory data

The summary of safety laboratory evaluations will be presented for the groups of laboratory tests (e.g. hematology, clinical chemistry). Descriptive summary statistics for the change from baseline to each study visit will be presented. These descriptive summaries will be presented by test group, laboratory test and treatment group. Change from baseline will only be summarized for patients with both baseline and post baseline values. Relative and absolute frequencies of patients with liver events as defined in [Appendix 2](#) will also be provided, as well as shift tables based on the normal laboratory ranges. For the shift tables, the normal laboratory ranges will be used to evaluate whether a particular laboratory test value was normal, low, or high for each visit value relative to whether or not the baseline value was normal, low, or high. These summaries will be presented by laboratory test category and treatment group.

The number and percentage of patients with clinically notable laboratory results after baseline will be presented. Clinically notable laboratory results, for those parameters where ranges are available. Only patients with laboratory results within the normal reference range from the central laboratory at baseline will be included in the tabulations.

Safety laboratory parameters which are also part of the efficacy analyses will be included in the safety tables as well (e.g. liver enzymes, lipids).

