Vital signs		Notable abnormalities	
		Absolute	Relative to baseline
Pulse rate (beats/min)		> 130 < 40	> 120 and increase from baseline ≥ 15 ≤ 50 and decrease from baseline ≥ 15
Blood pressure (mmHg)	Systolic	> 200 < 75	≥ 180 and increase from baseline ≥ 20 ≤ 90 and decrease from baseline ≥ 20
	Diastolic	> 115 < 40	≥ 105 and increase from baseline ≥ 15 ≤ 50 and decrease from baseline ≥ 15

Note: these notable ranges should not be used as reference ranges to establish a clinical diagnosis

[figure not shown]

14 Appendix 2: Liver Monitoring and Follow-up Requirements

For transaminases (ALT, AST, GGT) and bilirubin, the baseline value will be calculated as the mean of the last two assessments before first administration of the study drug, which are usually those taken at the Screening 2 and Baseline visit.

Table 14-1 Management of Subjects with Confirmed ALP, ALT, AST, or Bilirubin Elevations With or Without Liver Related Clinical Symptoms

Baseline	Treatment-Emergent (Confirmed ^a)	Liver-Related Clinical Symptoms ^b	Action taken	
			Monitoring ^c	Study Drug
ALT and/or AST				
Baseline ALT and/or AST < 2 × ULN	ALT and/or AST > 3 × ULN but ≤ 5 × baseline	None	Laboratory monitoring and causality evaluation	Continue dosing
		Present	Comprehensive clinical evaluation and laboratory monitoring, as well as causality evaluation ^d , [REDACTED]	Interrupt dosing ^e
	ALT and/or AST > 3 × ULN but ≤ 5 × baseline AND total bilirubin > 2 × ULN (in Gilbert's syndrome, see footnote ^f)	With or without liver-related clinical symptoms	Comprehensive clinical evaluation and laboratory monitoring, as well as causality evaluation ^d , [REDACTED]	Interrupt dosing ^e
	ALT and/or AST > 3 × ULN and > 5 × baseline	With or without liver-related clinical symptoms	Comprehensive clinical evaluation and laboratory monitoring, as well as causality evaluation ^d , [REDACTED]	Permanently discontinue
Baseline ALT and/or AST ≥ 2 × ULN	ALT and/or AST > 2 × baseline but ≤ 3 × baseline	None	Laboratory monitoring and causality evaluation	Continue dosing
		Present	Comprehensive clinical evaluation and laboratory monitoring, as well as causality evaluation ^d , [REDACTED]	Interrupt dosing ^e
	ALT and/or AST > 2 × baseline but ≤ 3 × baseline AND total bilirubin > 2 × ULN ^f	With or without liver-related clinical symptoms	Comprehensive clinical evaluation and laboratory monitoring, as well as causality evaluation ^d , [REDACTED]	Interrupt dosing ^e

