
ALP = alkaline phosphatase; ALT = alanine aminotransferase; AST = aspartate aminotransferase; eCRF = electronic case report form; INR = international normalized ratio; [REDACTED]; ULN = upper limit of normal
 
^a The required confirmatory measurement should be obtained within 48 to 72 hours after the laboratory results become available. If prompt evaluation is not possible, study drug should be interrupted immediately (date of last study drug dose must be recorded in the eCRF).
 
^b Combination of clinical symptoms of abdominal pain, worsening or new fatigue, anorexia, nausea, rash, vomiting, diarrhea, fever, pruritus, and/or eosinophilia (> 5%).
 
^c Frequent hepatic laboratory testing and clinical assessments, including a thorough causality evaluation, should be performed every other week at minimum, in consultation with the sponsor, until resolution of clinical symptoms and/or stabilization of liver biochemistries to baseline levels or baseline grade of abnormality.
 
^d The sponsor should be notified of laboratory abnormalities and any clinical symptoms, and subjects should be closely monitored until resolution of clinical symptoms/stabilization of liver biochemistries to baseline levels or baseline grade of abnormality.
 
^e Study drug must be interrupted (date of last study drug dose must be recorded in the eCRF). The sponsor should be notified of laboratory abnormalities and any clinical symptoms, and subjects should be closely monitored until resolution of clinical symptoms/stabilization of liver biochemistries to baseline levels or baseline grade of abnormality. In subjects with elevations in liver biochemistry but who do not meet permanent drug discontinuation criteria, study drug may be resumed if it is determined that complete resolution to normal or clinically comparable to baseline levels or baseline grade of abnormality (baseline value will be calculated as the mean of the last two assessments before first administration of the study drug, which are usually those taken at the screening 2 and baseline visit) has occurred and it is not considered that the deterioration in liver function was related to study drug. This must be documented based on biochemical parameters and clinical symptoms, per the discretion of the investigator and in consultation with the sponsor. Restarting study drug is only permitted following an interruption of less than 28 days (see Section 5.5.5). If significant liver abnormalities recur at any time after restarting study drug, then study drug must be permanently discontinued.
 
^f In subjects with Gilbert's syndrome, in place of the total bilirubin criterion, use direct bilirubin > 2 × baseline.
 
^g Development of liver-related clinical symptoms in absence of biochemical abnormalities is an indication for prompt biochemical and physical evaluation to decide whether continued dosing is appropriate. If prompt evaluation is not possible, study drug should be interrupted and subject followed for laboratory monitoring and causality evaluation.
				

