
15 Appendix 3: Specific Renal Alert Criteria and Actions

Table 15-1 Specific Renal Alert Criteria and Actions

Serum Event	
Serum creatinine increase 25 – 49% compared to baseline	Confirm 25% increase after 24-48h Follow up within 2-5 days
Acute Kidney Injury: Serum creatinine increase \geq 50% compared to baseline	Follow up within 24-48h if possible Consider study treatment interruption Consider patient hospitalization /specialized treatment
Urine Event	
New dipstick proteinuria \geq 1+	Confirm value after 24-48h
Albumin- or Protein-creatinine ratio increase \geq 2-fold	Perform urine microscopy
Albumin-creatinine ratio (ACR) \geq 30 mg/g or \geq 3 mg/mmol;	Consider study treatment interruption / or discontinuation
Protein-creatinine ratio (PCR) \geq 150 mg/g or $>$ 15 mg/mmol	
New dipstick glycosuria \geq 1+ not due to diabetes	Blood glucose (fasting) Perform serum creatinine, ACR
New dipstick hematuria \geq 1+ not due to trauma	Urine sediment microscopy Perform serum creatinine, ACR
For all renal events:	
Document contributing factors in the eCRF: co-medication, other co-morbid conditions, and additional diagnostic procedures performed	
Monitor patient regularly (frequency at investigator's discretion) until either:	
Event resolution: sCr within 10% of baseline or protein-creatinine ratio within 50% of baseline, or	
Event stabilization: sCr level with \pm 10% variability over last 6 months or protein-creatinine ratio stabilization at a new level with \pm 50% variability over last 6 months.	

17 Appendix 5: The American Heart Association (AHA) Recommended Diet

Optimization of diet can result in a marked triglyceride-lowering effect that ranges between 20% and 50%. Good practices include weight loss, reducing simple carbohydrates at the expense of increasing dietary fiber, eliminating industrial-produced trans fatty acids, restricting fructose and saturated fatty acids, implementing a Mediterranean-style diet, and consuming marine-derived omega-3 PUFA.

AHA recommends the following:

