### **Adverse events of special interest / grouping of AEs**

Adverse events of special interest are the risks as described for both tropifexor and CVC (those that appear in tropifexor Development Safety Profiling Plan or CVC Investigator's Brochure, respectively). These will be summarized with absolute and relative frequency overall and by type of risk / AE.

Relative and absolute frequencies of patients with liver and renal events (see protocol Appendix 2 and 3, respectively) will also be provided.

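### SAP 5.3.1 counts liver and renal events as defined in protocol Tables 14-1 and 15-1, but ignores confirmation and, on its natural reading, the cause qualifiers

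*SAP*

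**What the plan says.** **Where the counts are promised.** SAP 2.8.1, under adverse events of special interest, states: "Relative and absolute frequencies of patients with liver and renal events (see protocol Appendix 2 and 3, respectively) will also be provided". For liver, protocol 9.5.2.2 had already promised "Relative and absolute frequencies of patients with liver events as defined in" Appendix 2.

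**How the SAP counts them.** SAP 5.3.1 has a two-part scheme for each organ; for the kidney it says "Renal laboratory events will be classified in two ways". One part is the protocol table and the other is an internal sponsor plan that is not in the documents. For the protocol tables the rule, given once for Table 14-1 and again for Table 15-1, is "Only the laboratory results criteria will be considered. Confirmation of the results is not taken into account".

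**How the protocol defines them.**
- Liver (Appendix 2): Table 14-1 is titled "Management of Subjects with Confirmed ALP, ALT, AST, or Bilirubin Elevations" and so on, its treatment-emergent column is marked as confirmed, and its footnote a reads "The required confirmatory measurement should be obtained within 48 to 72 hours after the laboratory results become available". The ALP rows exclude rises explained by known bone pathology.
- Creatinine (protocol 7.4): a rise of at least 25%, confirmed after at least 24 hours, "compared to baseline during normal hydration status".
- Renal table (Appendix 3, Table 15-1): new glycosuria counts only if "not due to diabetes", and new hematuria only if trauma is not the cause. Confirmation of the 25-49% creatinine rise appears here as an action, not as part of the criterion.

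SAP Section 4 lists three changes to the protocol analyses. This is not one of them.

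**The concern.** The label and the algorithm disagree. A reader of the study report will take the table to show the protocol's events, but it will show any single value over a threshold.

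This matters because safety is the primary objective and is judged descriptively. With no hypothesis test, the tabulated rates are what the reader weighs, and SAP 3.1 notes that one patient is 2% of an arm of 50. Liver and kidney are also the organs of interest: protocol 3.6 lists liver effects and renal function abnormalities among the potential toxicities of tropifexor.

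Two features make background counts likely:
- Protocol 1.1 describes type 2 diabetes as a usual companion of this disease. Only HbA1c of 9% or more is excluded (criterion 13), and oral antidiabetics and GLP-1 agonists are allowed at a stable dose (Table 5-4). New glycosuria from diabetes is foreseeable.
- Creatinine is compared with a single baseline value, whereas ALT, AST, GGT and bilirubin use the mean of two (SAP 2.1). Noise in that one value carries into every later comparison for the patient.

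**Working it through.** The plan gives no figure that depends on this rule, so there is nothing to reproduce. The text comparison establishes the point; the arithmetic only shows what size is possible. The CVs, per-visit rates and diabetes shares below are assumptions, because the documents give none.

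**1. Which elements the SAP rule drops**
- Liver confirmation: part of the event in Table 14-1, dropped explicitly.
- Creatinine confirmation: part of the event in protocol 7.4, an action in Table 15-1, dropped explicitly.
- Diabetes, trauma, bone pathology and hydration: none is a laboratory result, so a rule confined to laboratory criteria leaves them out. This is an inference. No other SAP section restores them.
- New onset: kept. Glycosuria already present at baseline is not counted.

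**2. Creatinine rise of at least 25% from noise alone**

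Table 6-1 schedules nine post-baseline creatinine visits (weeks 4, 8, 12, 16, 24, 32, 40, 48 and 52). Take log-normal values with no true change and σ = √ln(1 + CV²). Given a baseline error b ~ N(0, σ²), one visit is flagged with probability q(b) = 1 − Φ((ln 1.25 + b)/σ), where ln 1.25 = 0.223. Averaging over b:
- unconfirmed: E[1 − (1 − q(b))⁹]
- confirmed by an independent repeat against the same baseline: E[1 − (1 − q(b)²)⁹]

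By numerical integration:

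| CV | σ | Unconfirmed | Confirmed | Patients of 50 |
|---|---|---|---|---|
| 5% | 0.050 | 0.6% | 0.03% | 0.3 vs 0.02 |
| 7% | 0.070 | 7.3% | 1.1% | 3.6 vs 0.5 |
| 10% | 0.100 | 25.7% | 7.3% | 12.9 vs 3.7 |

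The excess caused by ignoring confirmation is the difference: about 0.3, 3.1 and 9.2 patients of 50.

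**3. Liver tests**

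Table 6-1 has ten post-baseline liver-test visits. With an assumed spurious rate q per visit, unconfirmed is 1 − (1 − q)¹⁰ and confirmed is 1 − (1 − q²)¹⁰. For q = 0.5%, 1% and 2% this gives 4.9%, 9.6% and 18.3% against 0.02%, 0.10% and 0.40%. It is an illustration only. The ALT and AST limits are multiples of the upper limit of normal or of baseline, so the true q may be lower than this range, and a repeat 48 to 72 hours later is not fully independent.

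**4. Glycosuria**

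Extra patients per arm = 50 × D × g, where D is the diabetic share and g the proportion of diabetic patients who develop new glycosuria of 1+ or more. D = 30% and g = 10% gives 50 × 0.3 × 0.1 = 1.5; D = 70% and g = 30% gives 50 × 0.7 × 0.3 = 10.5.

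**5. Dilution**

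A background rate β common to all arms turns a true rate p into 1 − (1 − p)(1 − β). Assume 4% against 14%, a ratio of 3.5.
- β = 10%: 1 − 0.96 × 0.90 = 13.6% and 1 − 0.86 × 0.90 = 22.6%, ratio 1.66.
- β = 20%: 23.2% and 31.2%, ratio 1.34.

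The risk difference shrinks less, from 10 points to 9 and 8.

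**The case against.** **The rule is disclosed and sensitive by design.** It applies equally to blinded arms and feeds descriptive tables. For the first study of this combination in patients with biopsy-confirmed NASH, an any-value count is a defensible screen. This stands, and it is why the count should be kept. It does not justify presenting that count as the protocol's confirmed events.

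**The renal case is weaker than the liver case.** In Table 15-1, the table the SAP cites, creatinine confirmation is an action. The visible protocol Section 9 promises liver-event frequencies only, and the renal table comes from the SAP. This stands: the renal conflict on confirmation is with protocol 7.4, and the omission from SAP Section 4 can be held against the liver table only.

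**Dropping the cause qualifiers is inferred.** The laboratory-only sentence may have been meant to set aside the symptom column of Table 14-1. That is possible for liver, but the same sentence is applied to Table 15-1, which has no symptom column. There, the non-laboratory parts of the criteria are the diabetes and trauma qualifiers. The inference is the natural reading, though not a stated rule.

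**Other safeguards exist.** Abnormal values become adverse events only on clinical grounds (protocol 7.1), possible drug-related liver injury is adjudicated blind (7.3, 8.5), and shift tables and changes from baseline are reported. The second classification may handle confirmation, but it cannot be checked. All this limits the harm without correcting the table.

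**A confirmed count can mislead too.** If prompt re-evaluation is impossible, study drug is interrupted (Table 14-1, footnote a), so a later normal value may reflect resolution off drug. A row confirmed by whatever value came next would lose such rises. This stands and shapes the fix.

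**Conclusion.** The point holds as a mismatch between label and algorithm. For liver, the SAP departs from the confirmed events that protocol 9.5.2.2 says will be tabulated, and does not list the change. For creatinine it departs from protocol 7.4. By its natural reading it also counts new glycosuria in diabetic patients, which Table 15-1 excludes.

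A reader might infer more than the documents support:
- *That these become drug-safety events.* The SAP calls them laboratory events and attributes none to drug.
- *That every qualifier is removed.* New onset is kept, and only confirmation is named as dropped.
- *That one arm is favoured.* The rule is the same in every arm, so the expected effect is higher counts throughout and diluted contrasts. A chance imbalance in diabetes between arms of about 50 could push the glycosuria counts either way, but that is noise, not systematic bias.
- *That these tables carry the safety comparison.* They are one descriptive output beside adverse events, laboratory changes and adjudication.

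The size cannot be fixed from the documents. Unconfirmed creatinine flags from noise run from about 0.3 to 13 of 50 patients over CVs of 5% to 10%, and glycosuria adds 1.5 to 10.5 per arm over the assumed range. The effect could be negligible or large enough to obscure a real difference. The correction is cheap and should be made, but no hypothesis test or sample size depends on it.

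**What to change.** In SAP 5.3.1 and the matching table shells:

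1. Keep the any-value count and label it *unconfirmed laboratory threshold*.
2. Beside it, add a row of confirmed events, using the repeat taken in the protocol's confirmation window where one exists. Show patients with no repeat available on their own line. Still count rises whose repeat was taken after study drug was interrupted, so that resolution off drug does not remove them.
3. State which window is used. For liver the protocol gives 48 to 72 hours. For creatinine, 7.4 says at least 24 hours and Table 15-1 says 24-48 hours; these passages must be reconciled for the analysis.
4. Show new glycosuria separately for patients with and without diabetes, identified from medical history or antidiabetic medication, and drop neither group. State in the SAP whether the trauma, bone-pathology and hydration qualifiers are applied.
5. List the liver departure in SAP Section 4.

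No new data are needed. Unplanned liver, creatinine and urinalysis results (protocol Section 6), medical history (6.2.2) and medications (5.5.7, 6.2.5) are already recorded. The cost is a little programming and a longer table.
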